There are significant unmet needs for just about every clinical aspect of the patient with cluster headache, particularly related to the severity of the disease and treatment options. The majority of patients experiencing cluster headache attacks rate their pain intensity as near to or at the worst pain imaginable (using a Visual Analog Scale 10-cm scale; Torelli and Manzoni 2003). The verbatim descriptors of the pain experienced by patients are varied and complex, including drill; point; needle; punch; spear; stab wound; knife wound; stinging; piercing; shooting; hammer; pangs; throbbing; pulsating; and rhythmic (Torelli and Manzoni 2003). In the United States, there is only one approved abortive medication (treatment initiated at the start of the attack to shorten the overall duration of the attack); limited to only twice-daily use, and no approved preventive medications. The desperation in this patient population is exemplified by approximately half of patients reporting self-injurious behavior during attacks (Rozen and Fishman 2012) and many patients turning to illicit drug use, such as marijuana, cannabinoids, and hallucinogens (psilocybin, LSD, and 2-Bromo LSD), in an attempt to alleviate their suffering (Karst et al. 2010; McGeeney 2012; Tepper and Stillman 2013).

Increased plasma or serum levels of calcitonin gene-related peptide (CGRP) have been associated with painful syndromes such as migraine and cluster headache (Edvinsson and Goadsby 1994). Calcitonin gene-related peptide is a 37-amino acid neuropeptide member of a family of peptides that includes amylin, adrenomedullin and calcitonin, is one of the most abundant peptides within the nervous system (McCarthy and Lawson 1990), and is highly expressed in trigeminal ganglion neurons. The association of CGRP with cluster headache was initially demonstrated in a study of patients with spontaneous cluster headache attacks who were

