10.2.2.2. Vital Signs

Blood pressure and pulse will be collected in triplicate at every scheduled and unscheduled office visit as specified in the Study Schedule ([Attachment 1](#)). All sites will be provided with an automated blood pressure machine with several cuff sizes. The following guidelines will be used by investigative sites when measuring vital signs:

- Blood pressure and pulse must be measured before any blood draws.
- Blood pressure will be measured in sitting position with both feet resting on the floor after the patient has rested for at least 5 minutes.
- Blood pressure will be measured with a cuff that is appropriate to the size of the patient.
- Use the same arm for blood pressure collection throughout the study.
- Arm with cuff must be supported at approximately the heart level.
- Three sitting blood pressures and pulse measurements will be collected at approximately 30 to 60 second intervals.

10.2.2.3. Columbia-Suicide Severity Rating Scale, Self-Harm Supplement Form, and Self-Harm Follow-up Form

The C-SSRS and Self-Harm Supplement Form (SHSF) will be administered to assess and evaluate patients for suicide-related events (behavior and/or ideation) at every scheduled and unscheduled office visit as specified in the Study Schedule ([Attachment 1](#)). The C-SSRS captures the occurrence, severity, and frequency of suicide-related thoughts and behaviors during the assessment period (Posner et al. 2011). The scale includes suggested questions to solicit the type of information needed to determine if a suicide-related thought or behavior occurred. The SHSF captures the number of discrete events of suicidal behavior, possible suicidal behavior, or nonsuicidal self-injurious behavior and must be completed at every visit. Additionally, the Self-Help Follow-up Form (SHFU) will be completed at any visit, including screening/baseline visits, when a suicidal or non-suicidal self-injurious behavior is identified. At any time during the study, if a patient is considered to be at significant risk for suicide by the investigator, prompt referral of the patient to a mental health professional should be considered.

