- Since the originally planned interim analysis for sample size re-estimation will not be conducted due to enrollment infeasibility, all languages and methodology descriptions related to sample size increase are removed.
- In Section 5.8, reports to be generated were updated to reflect that analyses from all SPs specified in this SAP will be performed at the interim analysis instead of only performing analyses for SP III. However, the analyses conducted for SP III will be deemed final since all patients will complete SP III at the interim analysis. The analyses using data from SP IV will be rerun and updated when the completed data are available at the final database lock.
- An appendix of important protocol deviations was added.
- Other minor corrections, modifications, and clarifications were made.

Statistical Analysis Plan Version 5 has been approved prior to the interim analysis (the first and final assessment of primary efficacy endpoint after all patients completed double-blind phase, which is the first unblinding to study team). There is no modification to the primary analysis methodologies for the primary, key secondary, and other secondary efficacy endpoints. The changes incorporated in Version 5 are summarized as follows:

- In Section [5.4.1.2](#), the exploratory endpoint for cluster headache attack duration was modified from “average weekly cluster headache attack minutes per attack for the remaining cluster headache days” to “weekly total cluster headache attack duration.” An exploratory responder endpoint for the weekly total cluster headache attack duration that is defined as 30% or greater reduction is also added.
- In Section [5.5.9.1.2](#), removed the requirement of needing at least 4 events occurred in at least one treatment to display p-value.
- In [Table CGAL.5.4](#), added additional patient populations for analysis of treatment-emergent, potentially clinically significant changes and sustained elevation in vital signs.
- In Section [5.5.10](#), additional subgroup variables were added for subgroup analysis.

CCI

- In the table of Description of Important Protocol Deviations in [Appendix 1](#), updated the data source of the Important Protocol Deviations (IPDs) to only display the final data source for the IPD analysis. Two new IPDs were added.

4. Study Objectives

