5.5.1.6. Baseline and Postbaseline Definition

Table [CGAL.5.2](#) describes the rules for determining the patient population and baseline and postbaseline observations for each study phase and type of analysis. When “last of Visit x-x” is used in the table, the last nonmissing observation obtained in the visit interval will be used.

Table CGAL.5.2. Patient Population with Baseline and Postbaseline Definitions by Study Phase and Type of Analysis

Study Phase/Analysis	Patient Population	Baseline Observation	Postbaseline Observation(s)
Study Phase III			
Continuous secondary efficacy analyses (Repeated measures)	Patients in ITT population with a baseline and at least 1 postbaseline observation	Visit 3	All Visits 4-7
TEAEs	Safety population	All Visits 1-3 before dosing	Visit 3 after dosing through Visit 7
SAEs, Discontinuations due to AEs	Safety population	NA	Visit 3 after dosing through Visit 7
C-SSRS categorical analyses	Patients in safety population with a baseline and at least one postbaseline C-SSRS assessment	Recent history: All Visits 1-3 excluding lifetime ^a All prior history: Visits 1- 3 including lifetime ^a	All Visits 3.01-7
TE abnormal laboratory values	Patients in safety population with normal laboratory values at all nonmissing baseline visits (with respect to direction being analyzed) and who have at least 1 postbaseline observation	All Visits 1-3	All Visits 3.01-7
TE immunogenicity	Patients in safety population who are evaluable for TE ADA	Visit 3	All Visits 3.01-7
TE changes in vital signs and weight, ECG parameters	Patients in safety population with a baseline and at least 1 postbaseline observation	Last nonmissing value from Visits 1-3 for BP, pulse, and ECG All Visits 1-3 for weight and temperature	Visits 3.01-7

Patient Population with Baseline and Postbaseline Definitions by Study Phase and Type of Analysis

Study Phase/Analysis	Patient Population	Baseline Observation	Postbaseline Observation(s)
Continuous safety analysis of vital signs, weight, laboratory, and ECG parameters (Box-whisker plot)	Safety population	Last non-missing value from Visits 1-3	Visits 4-7
Study Phase III and IV Combined			
TE immunogenicity	Patients in safety population who are evaluable for TE ADA	Visit 3	All Visits 3.01-9
Study Phase IV			
Post TEAEs	Posttreatment population	All Visits 1-7	All Visits 7.01-9
SAEs, Discontinuations due to AEs	Posttreatment population	NA	All Visits 7.01-9

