5.5.9.1. Categorical Safety Variables

Unless specified otherwise, the categorical safety analyses will include both scheduled and unscheduled visits and be conducted for SP III and SP IV separately.

Comparisons between treatment groups for all categorical safety measures will be made using Fisher's exact test for SP III with the safety population. Descriptive statistics only will be presented for the treatment groups in SP IV with post-treatment population.

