Upper respiratory tract infections will be defined using all the PTs from the 2 High Level Terms of “upper respiratory tract infections” and “upper respiratory tract infections NEC” as defined in MedDRA. The number and percentage of patients with TEAEs of upper respiratory tract infections will be summarized by treatment group using MedDRA PTs. Events will be ordered by decreasing frequency in the galcanezumab 300 mg group.

The number and percentage of patients with TEAEs of upper respiratory tract infections by maximum severity will be summarized by treatment group using MedDRA PTs. For each patient and upper respiratory tract infection event, the maximum severity for the MedDRA level being displayed (PT) is the maximum postbaseline severity observed from all associated LLTs mapping to that MedDRA level.

By-subject listings of treatment-emergent upper respiratory tract infections and upper respiratory tract infections leading to study drug discontinuation will be provided.

5.5.9.1.2. *Suicide-Related Thoughts and Behaviors*

Postbaseline suicidal ideation, suicidal behavior, and self-injurious behavior without suicidal intent occurring during SP III, based on the C-SSRS, will be summarized by treatment. In particular, for each of the following events, the number and percent of patients with the event will be enumerated by treatment: completed suicide, nonfatal suicide attempt, interrupted attempt, aborted attempt, preparatory acts or behavior, active suicidal ideation with specific plan and intent, active suicidal ideation with some intent to act without specific plan, active suicidal ideation with any methods (no plan) without intent to act, nonspecific active suicidal thoughts, wish to be dead, and self-injurious behavior without suicidal intent. These measures will also be summarized for SP IV.

In addition, the number and percent of patients who experienced at least 1 of various composite measures during SP III and SP IV separately will be presented and compared. These include suicidal behavior (completed suicide, nonfatal suicidal attempts, interrupted attempts, aborted attempts, and preparatory acts or behavior), suicidal ideation (active suicidal ideation with specific plan and intent, active suicidal ideation with some intent to act without specific plan, active suicidal ideation with any methods [no plan] without intent to act, nonspecific active suicidal thoughts, and wish to be dead), and suicidal ideation or behavior.

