The number and percent of patients who experienced at least 1 of various comparative measures during treatment will be presented and compared for SP III and SP IV. These include treatment-emergent suicidal ideation compared to recent history, treatment-emergent serious suicidal ideation compared to recent history, emergence of serious suicidal ideation compared to recent history, improvement in suicidal ideation at endpoint compared to baseline, and emergence of suicidal behavior compared to all prior history.

Specifically, the following outcomes are C-SSRS categories and have binary responses (yes/no). The categories have been re-ordered from the actual scale to facilitate the definitions of the composite and comparative endpoints, and to enable clarity in the presentation of the results.

Category 1 – Wish to be Dead

Category 2 – Nonspecific Active Suicidal Thoughts

Category 3 – Active Suicidal Ideation with Any Methods (Not Plan) without Intent to Act

Category 4 – Active Suicidal Ideation with Some Intent to Act, without Specific Plan

Category 5 – Active Suicidal Ideation with Specific Plan and Intent

Category 6 – Preparatory Acts or Behavior

Category 7 – Aborted Attempt

Category 8 – Interrupted Attempt

Category 9 – Actual Attempt (Non-Fatal)

Category 10 – Completed Suicide

Self-injurious behavior without suicidal intent is also a C-SSRS outcome (although not suicide related) and has a binary response (yes/no).

Composite endpoints based on the above categories are defined below.

- Suicidal ideation: A “yes” answer at any time during treatment to any 1 of the 5 suicidal ideation questions (Categories 1 to 5) on the C-SSRS.
- Suicidal behavior: A “yes” answer at any time during treatment to any 1 of the 5 suicidal behavior questions (Categories 6 to 10) on the C-SSRS.
- Suicidal ideation or behavior: A “yes” answer at any time during treatment to any 1 of the 10 suicidal ideation and behavior questions (Categories 1 to 10) on the C-SSRS.

The following outcome is a numerical score derived from the C-SSRS categories. The score is created at each assessment for each patient and is used for determining treatment emergence.

- Suicidal Ideation Score: The maximum suicidal ideation category (1 to 5 on the C-SSRS) present at the assessment. Assign a score of 0 if no ideation is present.

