- An increase in the maximum suicidal ideation score to 4 or 5 on the C-SSRS during treatment (Visits 3.01 to 7 for SP III; Visits 7.01 to 9 for SP IV) from no suicidal ideation (scores of 0) during the screening and lead-in periods (C-SSRS scales taken at Visits 1 to 3 excluding “lifetime” for SP III; C-SSRS scales taken at Visits 1 to 7 excluding “lifetime” for SP IV). Recent history excludes “lifetime” scores from the Baseline C-SSRS scale or Baseline/Screening C-SSRS scale.
- Emergence of serious suicidal ideation compared to all prior history:
An increase in the maximum suicidal ideation score to 4 or 5 on the C-SSRS during treatment (Visits 3.01 to 7 for SP III; Visits 7.01 to 9 for SP IV) from no suicidal ideation (scores of 0) prior to treatment (C-SSRS scales taken at Visits 1 to 3 including “lifetime” for SP III; C-SSRS scales taken at Visits 1 to 7 including “lifetime” for SP IV).

- Improvement in suicidal ideation at endpoint compared to baseline: A decrease in suicidal ideation score at endpoint (the last measurement during treatment; Visits 3.01 to 7 for SP III; Visits 7.01 to 9 for SP IV) from the baseline measurement (the measurement taken just prior to that study phase (last nonmissing value taken at Visit 2 to Visit 3 for SP III; last nonmissing value taken at Visit 3.01 to Visit 7 for SP IV)).
- Emergence of suicidal behavior compared to all prior history: The occurrence of suicidal behavior (Categories 6 to 10) during treatment (Visits 3.01 to 7 for SP III; Visits 7.01 to 9 for SP IV) from not having suicidal behavior (Categories 6 to 10) prior to treatment (Visits 1 to 3 including “lifetime” for SP III; C-SSRS scales taken at Visits 1 to 7 including “lifetime” for SP IV).

Patients who discontinued from the study with no postbaseline C-SSRS value will be considered unevaluable for analyses of suicide-related events. Only evaluable patients will be considered in the analyses. Fisher’s exact test will be used for treatment comparisons in SP III.

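### Self-injurious behavior without suicidal intent is the one C-SSRS outcome type in SAP 5.5.9.1.2 with no baseline-referenced measure, so the SP III count can dilute new-onset harm if the behavior is common at baseline

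*SAP*

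**What the plan says.** SAP 5.5.9.1.2 opens with the rule for the whole scale: "Postbaseline suicidal ideation, suicidal behavior, and self-injurious behavior without suicidal intent occurring during SP III, based on the C-SSRS, will be summarized by treatment". Self-injurious behavior without suicidal intent is then named as a separate binary C-SSRS outcome, outside Categories 1 to 10. The composite and comparative endpoints that follow are built from Categories 1 to 5 (ideation) and 6 to 10 (suicidal behavior). Ideation has treatment-emergent and emergent versions, and suicidal behavior has emergence against all prior history. None of them covers this item.

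The item falls under a between-arm test by general rule. SAP 5.5.9.1 says "Comparisons between treatment groups for all categorical safety measures will be made using" Fisher's test in SP III, and 5.5.9.1.2 closes by saying that Fisher's "exact test will be used for treatment comparisons in SP III". The SAP revision history records that Version 5, for this section, "removed the requirement of needing at least 4 events occurred in at least one treatment to display p-value".

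A baseline is available. Table CGAL.5.2 defines two C-SSRS baseline windows. One reads "Recent history: All Visits 1-3 excluding lifetime", and the other includes lifetime, which is captured at Visit 1. Protocol 10.2.2.3 adds the Self-Harm Supplement Form, which captures "nonsuicidal self-injurious behavior and must be completed at every visit". The SAP plans no analysis of that form.

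The Protocol introduction (Section 5) describes the population as having "approximately half of patients reporting self-injurious behavior during attacks".

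**The concern.** A post-baseline *yes* on this item can come from a patient whose existing behavior continues or from a patient in whom it starts after dosing. The count by arm does not separate them. For most safety items the pre-existing part is small, but here the Protocol itself gives reason to think it might not be.

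The pre-existing part is also tied to attacks, and the drug is meant to reduce attacks. Recurrent self-injury may therefore behave partly as an efficacy outcome and fall on the drug arm, while any new-onset harm rises. The two parts then offset each other in a single rate. At stake is whether the safety tables could show an excess of new self-injury, in a population where self-harm is a recognised problem, when the data to separate the two parts are already collected.

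**Working it through.** There is no figure to reproduce. The documents give no expected rate for this item, and the sample size details are in a separate document to the ethical review board (SAP 5.2).

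**Inputs from the documents.** About 162 patients at 1:1, so 162/2 = 81 per arm (SAP 5.2). Two-sided 0.05 with no multiplicity adjustment for safety (SAP 5.5.1). Fisher's exact test in SP III (SAP 5.5.9.1 and 5.5.9.1.2). About half with self-injury during attacks (Protocol 5).

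**Assumed inputs.** Share with the behavior at baseline, b: 50%, 30% or 10%. Persistence, p: 80% on placebo, and 80% or 60% on drug. New onset in the others, e: 2% on placebo, 15% on drug.

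**Formulas.** On-treatment rate = b·p + (1−b)·e. Patients per arm without baseline behavior = 81·(1−b): 40.5, 56.7 and 72.9, taken as 40, 57 and 73. Power is the summed binomial probability of all pairs of counts with two-sided Fisher p ≤ 0.05. For example, at b = 50%:
- placebo: 0.5·0.80 + 0.5·0.02 = 41.0%
- drug, persistence 80%: 0.5·0.80 + 0.5·0.15 = 47.5%
- drug, persistence 60%: 0.5·0.60 + 0.5·0.15 = 37.5%

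| b | Drug persistence | Placebo rate | Drug rate | Power, planned count | Power, no baseline behavior (n per arm) |
|---|---|---|---|---|---|
| 50% | 80% | 41.0% | 47.5% | 10% | 36% (40) |
| 50% | 60% | 41.0% | 37.5% | 5% | 36% (40) |
| 30% | 80% | 25.4% | 34.5% | 20% | 60% (57) |
| 30% | 60% | 25.4% | 28.5% | 5% | 60% (57) |
| 10% | 80% | 9.8% | 21.5% | 46% | 77% (73) |
| 10% | 60% | 9.8% | 19.5% | 34% | 77% (73) |

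**Dilution.** With equal persistence the 13-point excess in new onset becomes (1−b)·13 points: 6.5, 9.1 and 11.7 points at shares of 50%, 30% and 10%.

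**Reversal.** The difference is (1−b)·13 − b·(fall in persistence), in points. It reaches zero when the fall equals 13·(1−b)/b: 13 points at 50%, 30.3 at 30%, and 117 (impossible) at 10%. The assumed fall of 20 points exceeds only the first. In that cell the planned count shows the drug numerically worse about 30% of the time, against 98% in patients without baseline behavior. The 5% in that row is not power to detect harm: in the same enumeration, 4.7 of 5.2 percentage points are rejections in the drug's favor.

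**Smaller excesses.** With 40 per arm without baseline behavior, power is 11% for 2% v 10% and under 1% for 2% v 5%.

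**The case against.** The strongest reply is that the planned count is a valid randomized comparison of total on-treatment self-injury, with baseline status balanced in expectation. That stands: nothing in it is biased for the question it answers. What is missing is a second view.

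A reader might infer from the Protocol's figure that new-onset harm will be swamped in this trial, or that the drug will look safer than it is. The documents do not support that. The figure is a literature self-report about behavior during attacks, with no instrument or recall period. It is not a C-SSRS rate at Visits 1-3, and the documents give none. Reversal also needs a sizeable fall in persistence: at a 30% share with persistence cut to 60%, the drug arm still looks worse (25.4% v 28.5%). The opposite inference, that the two analyses nearly agree when the behavior is uncommon at baseline, is also unsupported: at 10% the gap is 34-46% v 77%.

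Other points stand in part:
- The wording for this item is that it is summarized and enumerated. That it is tested follows only from the general Fisher rules.
- The SAP treats the item as not suicide related, and the safety objective names suicidal ideation and behaviors.
- Self-injury reported as an adverse event would pass through the baseline-referenced TEAE rule (SAP 5.5.9.1.1), but the SAP does not link the C-SSRS item to it.
- Recent history alone is an imperfect reference. The pre-randomization diary phase is 10 to 15 days, while SP III runs to about Day 60. A patient who self-injures only in some attacks could answer *no* at Visits 1-3 and *yes* later. The all-prior-history window answers this better, at the price of a smaller denominator.
- An emergent test is weak for modest excesses, so it should not displace the any-event comparison.

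**Conclusion.** The omission is real: this is the only C-SSRS outcome type in SAP 5.5.9.1.2 without a baseline-referenced measure, although the baseline is collected and its windows are defined. Its effect is conditional. If a substantial share of patients report the behavior on the C-SSRS at baseline, the SP III count dilutes new onset. If the drug also lowers recurrence, the count can hide the excess or, at a share near one half, reverse its sign.

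The sizes rest on assumed persistence and new-onset rates, and on the planned 81 per arm. The SAP revision history says enrollment was terminated before the target for the planned interim analysis, so actual numbers may be lower. The documents do not support calling the planned comparison invalid or replacing it. This is an inexpensive addition to a safety table.

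**What to change.** In SAP 5.5.9.1.2, add emergence of self-injurious behavior without suicidal intent for SP III: a *yes* at Visits 3.01-7 among patients with *no* at Visits 1-3. Show it against recent history (excluding lifetime) and against all prior history (including lifetime, the window already used for emergence of suicidal behavior). Report Fisher's exact test and the risk difference with 95% CI. Also show the any-event count split by baseline status. Keep the any-event comparison as planned, with the emergent measure beside it and not in its place.

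The cost is one definition and a few table rows from data already collected. The downside is a smaller denominator and low power for modest excesses (about 11% for 2% v 10% with 40 per arm), so the interval should carry the interpretation. A non-significant emergent test should not be read as absence of harm.

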									Phone visits (V4 and V6) are contacts between office visits to collect any spontaneously reported AE

CCI

RNA storage sample	X	X	X		X		X		Sample must be collected in a Tempus tube
PGI-I					X			X	
C-SSRS/SHSF, SHFU	X	X	X	X		X		X	To be completed at scheduled and unscheduled office visits
Recording of AEs	X	X	X	X	X	X	X	X	
Review Diary data				X		X		X	Following Informed Consent, patients are required to complete their diaries daily beginning on the day of their next cluster headache attack. Sites should review the diary compliance with the patient during office visits.
Concomitant medications	X	X	X	X	X	X	X	X	

Abbreviations: AE = adverse event; approx. = approximately; b/w = between; CGRP = calcitonin-gene related peptide; C-SSRS = Columbia-Suicide Severity Rating Scale; d = day; ECG = electrocardiogram; ePRO = electronic patient-reported outcome; ET = early termination; FSH = follicle stimulating hormone; hrs = hours; IP = investigational product; min = minute; PGI-I = Patient Global Impression of Improvement; Ph = phone; Pre-Rand. = pre-randomization; PK = pharmacokinetics; SHSF = Self-Harm Supplement Form; SHFU = Self-Harm Follow-Up Form; SP = Study Phase; V = visit; yr = year.

^a Selected tests may be obtained in the event of a treatment-emergent hepatic abnormality and may be required in follow-up with patients in consultation with the Lilly, or its designee, clinical research physician. See [Attachment 3](#) for more details regarding specific hepatic monitoring tests. If the patient has discontinued the trial and returns for hepatic follow-up, the site should use the 800 series as the visit designation.

Study Schedule, I5Q-MC-CGAL, SP IV-ET

Study Phase (SP)	SP IV		ET	Comments
Description	Post-treatment			
Interval (days) since previous office visit	60	60		
Interval allowance (days)	+/- 8	+/- 8		
Visit	8	9		
Visit Day	Day 120	Day 180	ET	
Month	4	6		
ECG		X	X	All ECGs should be collected prior to blood draws and dosing. Patients must be supine for approx. 5-10 min before ECG collection and remain supine but awake during ECG collection
Weight		X	X	
Vital signs	X	X	X	Vital signs will be taken at scheduled and unscheduled office visits and include body temperature, blood pressure, and pulse. Blood pressure and pulse will be measured in triplicate in the sitting position and should be measured prior to blood draws. Blood pressure will be assessed by utilizing a calibrated machine that will be provided to the sites.
Hematology		X	X	

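### The SAP's C-SSRS evaluability rule can drop a completed suicide that precedes any post-dose C-SSRS from the very table that lists completed suicide

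*SAP*

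**What the plan says.** SAP Section 5.5.9.1.2 sets out the C-SSRS-based enumeration by treatment group. The behavior events are "completed suicide, nonfatal suicide attempt, interrupted attempt, aborted attempt, preparatory acts or behavior". The section closes with the evaluability rule, "Patients who discontinued from the study with no postbaseline C-SSRS value will be considered unevaluable for analyses of suicide-related events", and then adds: "Only evaluable patients will be considered in the analyses".

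Table CGAL.5.2 carries the rule into the population definition. For SP III the population is "Patients in safety population with a baseline and at least one postbaseline C-SSRS assessment", with post-baseline defined as Visits 3.01 to 7. SP IV has the parallel requirement on the posttreatment population, with Visits 7.01 to 9.

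The protocol describes the same enumeration in Section 12.2.10.3 without any evaluability condition.

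On data collection, Protocol Attachment 1 says of the C-SSRS, SHSF and SHFU row: "To be completed at scheduled and unscheduled office visits". Within SP III the row is marked at Visits 3, 5 and 7, and afterwards at Visits 8 and 9 and at early termination (ET). Visits 4 and 6 are phone contacts and are not marked. Protocol Section 10.2.2.3 describes the companion form: "The SHSF captures the number of discrete events of suicidal behavior, possible suicidal behavior, or nonsuicidal self-injurious behavior".

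**The concern.** The table promises a count of completed suicides and attempts, but admits only patients who later have a C-SSRS. For a fatal event the condition works against the purpose: a death after first dose and before any post-baseline form leaves the patient unevaluable because of the event itself. Neither document makes an exception for an event known from another source.

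Suicidal ideation and behavior is a stated secondary safety objective (Protocol Section 6.2.2, SAP Section 4.2.2). The protocol's introduction also draws attention to self-harm in this disease, citing "approximately half of patients reporting self-injurious behavior during attacks". That phrase concerns self-injury during attacks and gives no suicide rate, so it is context only. What is at stake is a dedicated suicide table that could show zero completed suicides while the SAE table shows one, with no rule to reconcile them.

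**Working it through.** There is no figure of the plan's own to reproduce. The check sets the evaluability rule against the visit schedule and the discontinuation paths, and then sizes the effect.

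**Inputs**
- Visit 5: Day 30, allowance +5/-2 days, and no less than 28 days after Visit 3 (Protocol Attachment 1).
- Visit 8: 60 days after the previous office visit, allowance +/-8 days (Protocol Attachment 1).
- SP III runs nominally to Day 60 (Visit 7).
- Patients who stop IP early should enter SP IV; those who refuse have end-of-therapy procedures (Protocol Section 8.4.2). The ET column of Attachment 1 includes the C-SSRS.
- Planned size: about 162, randomized 1:1 (SAP Section 5.2).

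**Timing**
- First scheduled post-dose C-SSRS: 30 - 2 = 28 to 30 + 5 = 35 days after Visit 3, that is 28/60 = 47% to 35/60 = 58% of SP III.
- Visit 7 to Visit 8: 60 - 8 = 52 to 60 + 8 = 68 days.

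These are times to the next scheduled form. They are not periods without coverage, because a later C-SSRS looks back over its assessment period.

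**What happens to each patient under the literal rule**

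| Event | Next C-SSRS | Result in the suicide tables |
|---|---|---|
| Suicide after first dose, before any post-baseline C-SSRS | None, unless the site files one | Out of SP III numerator and denominator |
| Attempt, then withdrawal before Visit 5 | ET or unscheduled visit, treated as Visits 3.01 to 7 | Evaluable, can be counted in SP III |
| Same | Straight into SP IV, first form at Visit 8 | Absent from SP III; can appear only in descriptive SP IV output |
| Same | None done | Absent from both |
| Suicide between Visit 7 and Visit 8 | None, unless a form is filed or an unscheduled visit occurred | Out of the SP IV table; may be outside the posttreatment population altogether |

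The second row depends on a mapping the SAP does not give: Table CGAL.5.2 works in visit numbers and does not say which phase an ET assessment belongs to. The last row has a second cause: SAP Section 5.5.1 defines the posttreatment population by entry into a posttreatment visit, so the C-SSRS rule is not the only obstacle there.

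**Size at the planned number**

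Per arm: 162/2 = 81. Assume k early events in one arm, none in the other, and no post-baseline C-SSRS for the k patients. Kept rate = k/81; under the rule it becomes 0/(81 - k). The event counts are assumptions, for illustration only.

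| k | Events kept | Fisher p vs 0/81 | Under the rule |
|---|---|---|---|
| 1 | 1/81 = 1.2% (95% CI 0.03 to 6.7) | 1.00 | 0/80 |
| 2 | 2/81 = 2.5% | 0.50 | 0/79 |
| 3 | 3/81 = 3.7% | 0.25 | 0/78 |

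No test result turns on this. The count does.

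**The case against.** The strongest reply has five parts.

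First, a survivor who withdraws is due a C-SSRS at ET, at any unscheduled office visit, or at Visit 8. A reader might infer that every attempt leading to early withdrawal is excluded. The schedule does not support that; the attempt is lost only if none of these forms is completed. This stands.

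Second, the C-SSRS covers its whole assessment period (Protocol Section 10.2.2.3), so the 28 to 35 days are not unobserved for anyone with a later form. This also stands.

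Third, the C-SSRS is clinician-rated (Protocol Section 11.1), and no patient could answer its completed-suicide category. A site-completed form after a death would make the patient evaluable. It follows that exclusion is not certain, which a reader might otherwise conclude. But no passage asks for such a form, so the plan cannot rely on it.

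Fourth, the table is an instrument table by design, and the AE-based tables hold the event. In SP III, SAEs and discontinuations due to AEs use the full safety population with no C-SSRS condition, so an early suicide would be reported there as a death. This rules out any reading that the event is lost to the trial. It leaves two tables disagreeing on the gravest outcome. In SP IV the backstop is weaker, because the SAE table uses the posttreatment population too.

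Fifth, the effect is small. Exclusion Criterion 20 keeps out patients judged at significant risk of suicide. The SAP's revision history says enrollment ended early, so 81 per arm is a planning figure. Both are fair, and they limit the likelihood and precision of the problem without curing the rule.

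**Conclusion.** The point holds in a narrow form. Under the literal wording of SAP Section 5.5.9.1.2 and Table CGAL.5.2, a suicide after first dose and before any post-baseline C-SSRS drops from both numerator and denominator of the table that names it, unless a site files a form. A nonfatal attempt with withdrawal can be omitted if no further C-SSRS is done, or can shift to the descriptive SP IV output if Visit 8 is the first one. A death between Visit 7 and Visit 8 may also fall outside the posttreatment population.

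The consequence is an understated and inconsistent count, about 1 in 81 per arm per event at the planned size, and not a changed test. The conclusion rests on reading the evaluability rule as written, on the planned 1:1 split, and on there being no handling rule elsewhere. None appears in the two documents. The change is worth making because it is cheap and the outcome belongs to a stated safety objective.

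**What to change.** Amend SAP Section 5.5.9.1.2 and Table CGAL.5.2 as follows:

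- Count as evaluable, and as having the event, any safety-population patient with a completed suicide or nonfatal suicide attempt recorded after first dose in AE/SAE or SHSF/SHFU data, whether or not a post-baseline C-SSRS exists.
- Assign the event to the phase in which it occurred.
- Footnote every event whose source is not the C-SSRS, and state the denominator for each phase. This matters most in SP IV, where the patient may not belong to the posttreatment population.
- State which phase an ET C-SSRS belongs to.
- Keep the post-baseline C-SSRS requirement for ideation, for change-from-baseline endpoints, and for patients with no recorded event.

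The cost is a few lines of SAP text and a merge of records already collected. Most of the gain comes from the AE/SAE data, since the SHSF is completed at the same office visits as the C-SSRS. Limiting the rule to completed suicide and nonfatal attempt avoids having to map AE terms onto the aborted, interrupted and preparatory categories. The downside is a table that mixes sources and may report a slightly higher rate.
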